7.2 Dosing Symptoms as Adverse Events

Although signs and symptoms of allergic reaction, especially those that are mild in severity, are frequent and expected occurrences in response to dose escalation during OIT, they still constitute AEs. As such, the start and stop times of dose-related allergic reactions, as well as any therapeutic interventions and relatedness to IP, will need to be recorded (Section 7.6.1).

It is common for allergic reactions, especially allergic reactions to food allergens, to manifest with multiple symptoms. When multiple symptoms are noted during the same episode, it is up to the Investigator to determine whether one, or more than one, AE has occurred. For allergic / hypersensitivity reactions involving multiple symptoms, each individual symptom is to be entered on a separate log line on the AE eCRF. For each symptom, the AE eCRF will query “Is this an allergic reaction?” and the site should indicate yes/no accordingly.

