9.2.2 Secondary Endpoints

- Frequency of premature discontinuation of dosing due to AEs
- Frequency of premature discontinuation of dosing due to chronic/recurrent GI AEs
- Proportion of chronic/recurrent GI AEs resolving at 2, 4, and \geq 12 weeks following cessation of dosing
- Frequency of allergic reaction (hypersensitivity) AEs occurring during up-dosing, normalized for duration of treatment
- Frequency of anaphylaxis as defined in the protocol
- Frequency of use of epinephrine as a rescue medication
- Frequency of accidental ingestion of peanut and other allergenic foods and severity of any resultant reactions

- Assessment of asthma control using the ACT questionnaire and frequency of use of asthma rescue medication (short acting beta-agonists) in subjects with asthma

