### 4.2 Secondary Endpoints

Secondary endpoints are as follows:

- Frequency of premature discontinuation of dosing due to adverse events
- Frequency of premature discontinuation of dosing due to chronic/recurrent gastrointestinal (GI) adverse events
- In subjects who discontinue study early due to chronic/recurrent GI AEs, proportion whose ongoing GI adverse events resolved prior to 2, between 2 and 4, between 4 and 12, and  $\geq$  12 weeks following cessation of dosing
- Frequency of allergic reaction (hypersensitivity) adverse events occurring during up-dosing, normalized for duration of treatment
- Frequency of anaphylaxis as defined in the protocol
- Frequency of use of epinephrine as a rescue medication
- Frequency of ingestion of peanut (not study product) and other allergenic foods and severity of any resultant reactions
- Assessment of asthma control using the Asthma Control Test (ACT) questionnaire and frequency of use of asthma rescue medication (short acting beta-agonists) in subjects with asthma
- Frequency of adverse events that lead to early withdrawal

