### **9.8.1 Adverse Events**

All adverse events recorded on the adverse event case report form, symptoms recorded on the allergic adverse events case report form, and symptoms recorded on the in-clinic dosing case report will be summarized together.

If symptoms are recorded as part of an anaphylaxis reaction as reported on the Allergic AE or in-clinic dosing form, only the single anaphylaxis reaction event will be summarized and not the individual symptoms.

All reported adverse events will be classified into SOC and preferred term using MedDRA version 19.1.

Treatment-emergent adverse events are defined as those adverse events with onset after the first dose of study product. Adverse events with onset prior to first dose of study product will be included in subject listings, but not summarized. Treatment-emergent adverse events and non-treatment-emergent adverse events will be listed separately. Treatment-emergent adverse events will be summarized for the safety population by age group (4-11 years, 12-17 years, 4-17 years), treatment group (AR101, placebo), and by study period as follows:

- Initial escalation: All events beginning after the first dose of study product on day 1 and prior to the first administration of study product at home. To avoid gaps between study periods, the first administration of study product at home is assumed to be the day after at-home study product was dispensed at Initial Escalation Day 2.
- Up-dosing: All events beginning after the first administration of study product at home during up-dosing and prior to the first dose of 300 mg at home. To avoid gaps between study periods, the first administration of 300 mg at-home dose is assumed to be the day after the clinic visit where 300 mg dose was first tolerated and at-home 300 mg study product was dispensed.
- 300 mg QD: All events beginning after the first dose of 300 mg at home and prior to exit from the study.
- Overall: Across initial escalation, up-dosing, and 300 mg QD periods (first dose to last dose).

Summaries displayed by SOC and preferred terms will be ordered by descending incidence of SOC and preferred term within each SOC. Summaries displayed by preferred term only will be ordered by descending incidence of preferred term. Summaries of the following types will be presented:

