- Overall summary of number of unique treatment-emergent adverse events and treatment-emergent serious adverse events, subject incidence of treatment-emergent adverse events and treatment-emergent serious adverse events meeting various criteria, and exposure-adjusted incidence rates of treatment-emergent adverse events and treatment-emergent serious adverse events meeting various criteria, where exposure incidence rates are defined as the total number of events divided by the total number of subject-years at risk; the total number of subject-years at risk is defined as total number of days for all subjects in the study period divided by 365.25.
- Subject incidence of treatment-emergent adverse events by SOC and preferred term.
- Subject incidence of treatment-emergent adverse events by preferred term.
- Exposure-adjusted event rates for the most frequent treatment-emergent adverse events (ie, treatment-emergent adverse events occurring in  $\geq 5\%$  of the safety population) by preferred term.
- Subject incidence of treatment-emergent adverse events by severity grade, SOC, and preferred term.
- Subject incidence of treatment-emergent adverse events related to study product by SOC and preferred term.
- Exposure-adjusted event rates for the most frequent treatment-emergent adverse events related to study product (ie, related treatment-emergent adverse events occurring in  $\geq 5\%$  of the safety population) by preferred term.
- Subject incidence of grade  $\geq 3$  severity treatment-emergent adverse events by SOC and preferred term.
- Subject incidence of grade  $\geq 3$  severity treatment-emergent adverse events related to study product by SOC and preferred term.
- Subject incidence of serious adverse events by SOC and preferred term.
- Subject incidence of treatment-emergent adverse events leading to discontinuation of study product by SOC and preferred term.
- Subject incidence of treatment-emergent adverse events associated with the use of epinephrine by SOC and preferred term.
- Subject incidence of hypersensitivity treatment-emergent adverse events by SOC and preferred term, where hypersensitivity treatment-emergent adverse events are those treatment-emergent adverse events from the allergic adverse event and in-clinic dosing case report forms.

- Subject incidence of hypersensitivity treatment-emergent adverse events related to study product by SOC and preferred term.

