- Exposure-adjusted event rates for hypersensitivity treatment-emergent adverse events by preferred term.
- Subject incidence of treatment-emergent adverse events associated with a non-study product food allergen exposure by SOC, and preferred term.
- Subject incidence of treatment-emergent adverse events leading to early discontinuation by SOC and preferred term.
- Subject incidence of treatment-emergent adverse events with onset < 90 minutes after study product dosing at the study site by SOC and preferred term.

At each level of summarization (eg, any adverse event, SOC, and preferred term), subjects experiencing more than 1 treatment-emergent adverse event will be counted only once within each study period. In the summary of treatment-emergent adverse events by severity grade, subjects will be counted once at the highest severity reported at each level of summarization. Adverse event data will be presented in data listings by age group, treatment group, subject, study period, and event. Treatment-emergent adverse events; serious adverse events; severe, life-threatening, or fatal adverse events; and adverse events leading to discontinuation, reduction, or interruption of the study product will be presented in separate data listings.

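### The exposure-adjusted rate for allergic reactions in up-dosing counts symptom lines for ordinary reactions but one event per anaphylaxis, and no planned table gives reactions per subject-year

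*SAP*

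**What the plan says.** The endpoint is worded almost identically in both documents. SAP 4.2 has "Frequency of allergic reaction (hypersensitivity) adverse events occurring during up-dosing, normalized for duration of treatment", and Protocol 9.2.2 matches it. Neither says whether the unit is the reaction or the symptom.

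Protocol 7.2 governs recording. It expects reactions with several symptoms: "It is common for allergic reactions, especially allergic reactions to food allergens, to manifest with multiple symptoms". It then gives two instructions side by side. On the number of adverse events in an episode, "it is up to the Investigator to determine whether one, or more than one, AE has occurred". For allergic reactions with several symptoms, "each individual symptom is to be entered on a separate log line on the AE eCRF".

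SAP 9.8.1 pools the adverse event form with the symptoms from the allergic adverse event form and the in-clinic dosing form. It collapses one kind of reaction only. For anaphylaxis, "only the single anaphylaxis reaction event will be summarized and not the individual symptoms". Hypersensitivity events are all treatment-emergent events from the two allergy forms. For the rate, "exposure incidence rates are defined as the total number of events divided by the total number of subject-years at risk". The planned output for this endpoint is "Exposure-adjusted event rates for hypersensitivity treatment-emergent adverse events by preferred term", shown by study period, age group and arm.

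**The concern.** No rule groups the symptoms of a non-anaphylactic reaction into one reaction. A four-symptom reaction not reported as anaphylaxis adds four events, and the same four symptoms reported as anaphylaxis add one. The unit of count changes with the diagnosis.

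This is the only secondary endpoint in SAP 4.2 that is explicitly normalised for duration of treatment. A reader will take it as how often a child reacts per year of up-dosing, and the planned tables do not answer that. The rule also moves the wrong way: when more multi-symptom reactions meet the definition of anaphylaxis, the event count goes down.

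**Working it through.** The documents state no rate, ratio or event count for this endpoint, and SAP 5 says that no power-based sample size was calculated. There is no figure to reproduce, so the check writes out the counting rule.

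**Inputs.** From the documents: one line per symptom (Protocol 7.2), one event per anaphylaxis (SAP 9.8.1), and total events over subject-years (SAP 9.8.1). Not in the documents, hence assumed: λ, reactions per subject-year; s, mean symptom lines per non-anaphylactic reaction; a, the share of reactions that are anaphylaxis.

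**1. Within one preferred-term row.** A reaction normally adds at most one line to a given row, so the row approximates non-anaphylactic reactions featuring that symptom. If the symptom is equally common in both kinds of reaction, the row is (1 − a) times the full symptom rate. At an assumed a of 10% that is 0.90. If the symptom is more common in anaphylaxis, more is lost. Adding rows does not give reactions, because one reaction can appear in several rows.

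**2. An all-terms total, if one is produced.** Rate = λ × [(1 − a) × s + a].
- 100 reactions of 3 symptoms, no anaphylaxis: 100 × 3 = 300 events.
- The same 100 reactions, 10 classed as anaphylaxis: 90 × 3 + 10 = 280 events, a fall of 20/300 = 6.7%. There are still 100 reactions.

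**3. Comparison of arms on such a total.** The observed ratio equals the reaction-rate ratio times [(1 − aA) × sA + aA] / [(1 − aP) × sP + aP], with A for AR101 and P for placebo.
- Same s and a in both arms: factor 1.000.
- Same s in both arms (1 to 3), aA 0 to 10%, aP 0 to 2%: the factor runs from 2.8/3 = 0.933 to 3/2.96 = 1.014.
- s free to differ between arms (1 to 3 each), same ranges for a: the factor runs from 0.33 to 3.0.

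For illustration, assume 10 and 2 reactions per subject-year (ratio 5.00), with a of 5% and 1%:

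| s, AR101 / placebo | AR101 rate | Placebo rate | Ratio |
|---|---|---|---|
| 2 / 2 | 10 × (0.95 × 2 + 0.05) = 19.50 | 2 × (0.99 × 2 + 0.01) = 3.98 | 4.90 |
| 2 / 1.5 | 19.50 | 2 × (0.99 × 1.5 + 0.01) = 2.99 | 6.52 |
| 1.5 / 2 | 10 × (0.95 × 1.5 + 0.05) = 14.75 | 3.98 | 3.71 |

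Counting each reaction once returns 5.00 in every row.

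**4. Can another planned output supply the reaction rate?** Episode counts are planned for anaphylaxis (SAP 9.8.3), epinephrine use (9.8.4) and food allergy episodes (9.8.5), but not for ordinary reactions to dosing. Subject incidence (9.8.1) and the dose-level summaries (9.8.6 and 9.8.7) count each subject once, so they cannot give a frequency over time.

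**The case against.** The strongest reply is that the endpoint counts adverse events, and Protocol 7.1 and 7.2 treat allergic symptoms as adverse events in their own right. A symptom-level rate is then a permissible reading. That stands, and it rules out the stronger inference that the SAP plainly departs from its endpoint. It does not rescue the rule. On a symptom reading, anaphylaxis should not be collapsed; on a reaction reading, the other reactions should be. The rule fits neither.

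A reader might also infer that the comparison between arms is distorted, or that AR101 is made to look worse. The documents do not support this. Protocol 9 plans no hypothesis tests or between-group comparisons, the SAP plans no arm ratio for this endpoint, and symptoms per reaction and anaphylaxis share are not given for either arm. The error could go either way or be nil. With equal symptoms per reaction, the anaphylaxis rule alone moves the ratio by about 7% at most over the ranges above. The large factors also need an all-terms hypersensitivity total, which the SAP does not name: its overall summary refers to events meeting various criteria without listing hypersensitivity.

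Nor does the rule hide a worsening. Anaphylaxis is a separate secondary endpoint, and SAP 9.8.3 reports its number, severity, triggers, epinephrine use and individual symptoms by arm and period. A shift towards anaphylaxis would be visible there. Finally, the documents do not rank this endpoint above the other secondary ones.

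**Conclusion.** The point holds as a defect in the counting unit. The only planned exposure-adjusted output specific to this endpoint mixes symptom lines with whole anaphylaxis episodes, its rows omit symptoms within anaphylaxis, and no planned table gives reactions per subject-year. That follows from the text and needs no assumed value.

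Distortion between arms is a possibility only. It requires symptoms per reaction or the anaphylaxis share to differ between arms. Neither is documented, so no size or direction can be stated, and the figures above only illustrate the mechanism. It would affect a reader's descriptive comparison and no planned test. The change should be made, because a stated rule gives a number with no clear meaning and the repair is small.

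**What to change.** In SAP 9.8.1:
- State the counting unit for this endpoint.
- Define a reaction episode as all allergic symptom lines with onset inside one stated window, covering reactions to study product and to other triggers. SAP 9.8.4 sets a precedent with its 2-hour window, but that groups epinephrine doses, so the symptom window needs its own justification.
- Add rules for home doses split 8 to 12 hours apart (Protocol 6.5.5.2) and for missing onset times. SAP 7.2.1 imputes partial dates but gives no onset time to use.
- Count each episode once, whether or not it is anaphylaxis.
- Report episodes per subject-year in up-dosing by arm as the output for this endpoint, with a second window as a sensitivity check.
- Keep the preferred-term table as support, labelled as symptom-level with anaphylaxis symptoms excluded.

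The cost is one derivation and one table. Protocol 7.2 already asks for start and stop times of dose-related reactions, and the diary records dosing date and time (SAP 9.5). The downside is that any window is a convention, which the second window makes visible.

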### **9.8.2 GI Adverse Events**

Of subjects who discontinue due to chronic/recurrent GI adverse events, GI adverse events will be summarized by preferred term, study period, age group (4-11 years, 12-17 years, 4-17 years) and treatment group (AR101, placebo). Additionally, any of these subjects whose GI adverse events were ongoing will be further summarized as having events resolved prior to 2, between 2 and 4, between 4 and 12, and  $\geq$  12 weeks following cessation of dosing. Summaries will be provided using the safety population by age group (4-11 years, 12-17 years, 4-17 years) and treatment group (AR101, placebo).

All reported GI treatment-emergent adverse events for subjects who discontinue the study early due to chronic/recurrent GI AEs will be listed by age group, treatment group, subject, study period, and event and will include weeks to resolution following cessation of dosing for events that were ongoing.

### **9.8.3 Anaphylaxis**

All reported anaphylactic reactions will be listed by age group, treatment group, and subject.

Each anaphylactic reaction will be identified by the following triggers:

- Study product

- Peanut or peanut-containing food
- Other food allergen
- Medication
- Insect sting
- Environmental allergen(s)
- Other

Anaphylactic reactions will be summarized for the safety population by age group (4-11 years, 12-17 years, 4-17 years), and treatment group (AR101, placebo) for the following study periods:

- Overall (including initial escalation, up-dosing, 300 mg QD)
- Initial escalation
- Up-dosing
- 300 mg QD

The number of anaphylactic reactions, the number of anaphylactic reactions by trigger (study product, peanut or peanut-containing food, other food allergen, medication, insect sting, environmental allergen, and other), the number and percent of subjects experiencing an anaphylactic reaction by number of episodes, the number and percent of subjects experiencing an anaphylactic reaction by maximum severity using the Muraro grading scale ([Muraro, 2007](#); [Muraro, 2014](#)), the number and percent of subjects experiencing an anaphylactic reaction that was a serious adverse event, the number and percent of subjects experiencing an anaphylactic reaction that required epinephrine use, the location of epinephrine episodes (home or study site), and the number of subjects experiencing an anaphylactic reaction that involved individual symptoms will be summarized for each study period.

#### **9.8.4 Epinephrine Use as Rescue Medication**

Epinephrine use is defined as any medication with a preferred name of 'EPINEPHRINE' when coded as described in [Section 9.6](#).

All subjects per protocol are required to have epinephrine auto-injectors for use in case of a suspected anaphylactic reaction occurring outside the study site. There are differences in how and whether physicians record the prescription of epinephrine auto-injectors for PRN use. As a result, the presence or absence of a PRN prescription for epinephrine cannot be taken to indicate epinephrine usage, regardless of whether the prescription was written before or after study enrollment. The importance is counting the number of subjects receiving doses of epinephrine and the number of doses. As epinephrine should only be administered to treat a discrete allergic reaction, each dose of epinephrine should be closely temporally associated with a specific safety event and its use recorded as rescue medication on the concomitant medication case report form. In cases where a PRN epinephrine prescription is issued after the start of study product dosing, the study sites will be queried regarding if and when epinephrine was administered for a specific event.

The number and percent of subjects with at least 1 episode, where episode refers to 1 or more doses of epinephrine within a 2-hour window, will be summarized as well as the number of episodes experienced by each subject (1, 2, 3, and > 3). The total number of episodes will also be presented along with the number and percent of episodes by number of doses per episode, by associated adverse event severity, by seriousness of associated adverse events, by relatedness of associated adverse events, and by location of episode (home/study site). For subject counts, the number of subjects at risk within each study period will be used as the denominators. For unique episode counts, the total number of episodes within each study period will be used as the denominators. Data will be summarized for the safety population by age group (4-11 years, 12-17 years, 4-17 years), study period (initial escalation, up-dosing, 300 mg QD, overall), and treatment group (AR101, placebo).

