## 7 DEFINITIONS, DERIVATIONS, AND CONVENTIONS

### 7.1 Definitions and Derivations

- Study day is calculated as (assessment date – first dose date + 1) for assessments and visits performed on or after the first dose date, and (assessment date – first dose date) for assessments and visits prior to the first dose date.
- Baseline is defined as the last nonmissing value prior to the first dose of randomized study treatment in ARC007.
- Change from baseline is calculated as the observed value after the first dose – baseline value.
- The screening period is defined as the time beginning with the date and time of informed consent through the day prior to randomization.
- Initial escalation is defined as the time beginning with the date and time of the first dose of randomized study product at the study site and ending with the date of the last dose of randomized study product taken prior to up-dosing.
- Up-dosing is defined as the time beginning with the date and time of the first dose of study product at 3 mg at home, and ending with the date and time of first dose at

300 mg at the study site. Up-dosing will be approximately 20 weeks in duration, but may be extended to a maximum of 40 weeks to accommodate dose reductions and re-escalations, if necessary.

- A 300 mg QD period will be defined as the time beginning with the date and time of the first dose of study product at 300 mg at home and ending with the date of the last dose of study product. This period will be ideally approximately 2 weeks in duration at the end of ARC007, but dosing may continue up to a maximum of 48 weeks after day 1 to ensure tolerability of 300 mg prior to exiting ARC007. Some subjects continued to receive 300 mg doses in ARC007 after the expected rollover date while waiting for activation of ARC008 or ARC011 at the study site. The 300 mg doses as a result of the rollover delay will be included in the 300 mg QD period.

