#### **9.8.5 Food Allergy Episodes**

Food allergy episodes will be summarized for the safety population by age group (4-11 years, 12-17 years, 4-17 years), treatment group (AR101, placebo), and study period (initial escalation, up-dosing, and 300 mg QD, overall). For each period, the number and percent of subjects experiencing any food allergy episode, the number and percent of subjects experiencing a food allergy episode in response to peanut (or nonpeanut), the number and percent of subjects experiencing any food allergy episode that was a serious adverse event, the number and percent of subjects experiencing any food allergy episode that required treatment, and the total number of food allergy episodes (peanut and nonpeanut related) will be summarized. Further, subject incidence of food allergy, peanut-related food allergy, and nonpeanut-related food allergy will be displayed by the number of episodes experienced.

All reported food allergy episodes will be listed by age group, treatment group, and subject. Allergic reactions associated with foods other than peanut will be flagged.

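### Epinephrine and food allergy episodes are tabulated by study period with no person-time rate, although up-dosing lasts 20 to 40 weeks and 300 mg QD about 2

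*SAP*

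**What the plan says.** SAP 9.8.4 reports epinephrine use for initial escalation, up-dosing, 300 mg QD and overall. It gives subjects with at least one episode, subjects by number of episodes, and total episodes with several breakdowns. On denominators: "For subject counts, the number of subjects at risk within each study period will be used as the denominators". Episode percentages are taken out of all episodes in the period. SAP 9.8.5 uses the same periods: "For each period, the number and percent of subjects experiencing any food allergy episode", plus total episodes. Neither section names a rate per unit of time.

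SAP 7.1 sets the period lengths. "Up-dosing will be approximately 20 weeks in duration, but may be extended to a maximum of 40 weeks". The 300 mg QD period is ideally about 2 weeks but can run longer for tolerability, up to 48 weeks after day 1. In addition, "The 300 mg doses as a result of the rollover delay will be included in the 300 mg QD period". The length of that delay is not given.

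SAP 9.8.1 already defines an exposure-adjusted rate, events divided by subject-years, where "the total number of subject-years at risk is defined as total number of days for all subjects in the study period divided by 365.25". It applies the rate to an overall summary, to the most frequent adverse events (all and related), and to allergic events: "Exposure-adjusted event rates for hypersensitivity treatment-emergent adverse events by preferred term". For the two event types at issue it lists only head counts: "Subject incidence of treatment-emergent adverse events associated with the use of epinephrine by SOC and preferred term" and "Subject incidence of treatment-emergent adverse events associated with a non-study product food allergen exposure by SOC, and preferred term".

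**The concern.** A percentage of subjects with at least one event grows with time under observation. Placed side by side, a 20- to 40-week period and a 2-week period will show very different percentages even if the underlying rate is the same. A reader could conclude that the need for epinephrine, or reactions to food, falls once a child reaches 300 mg when the rate is unchanged or has risen. For a safety study that is the wrong direction in which to err. Because the rollover delay is unquantified, the reader cannot rescale by eye either.

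By-period description is a study aim. Protocol 2.2 asks for treatment-related events by study period, especially those of interest, and Protocol 7.3.4 names events associated with epinephrine among them. For food episodes the basis is the secondary endpoint on frequency of ingestion (SAP 4.2).

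Anaphylaxis in SAP 9.8.3 has the same layout but needs no change. Reactions on the allergic adverse event and in-clinic dosing forms are counted as single events and fall within the hypersensitivity rates of SAP 9.8.1.

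**Working it through.** **Period lengths.** Protocol Table 2 has ten dose levels from 3 to 240 mg, each for 2 weeks, before the first 300 mg dose: 10 × 2 = 20 weeks, matching the stated minimum. The maximum is 40 weeks. Up-dosing is therefore 10 to 20 times as long as a 2-week 300 mg QD period.

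**Assumptions (not in the documents).** Poisson episodes at a constant rate r = 0.3 per subject-year (range 0.1 to 0.5). 20% of children leave evenly through up-dosing, close to the 6 of 29 AR101 withdrawals in ARC001 (Protocol 1.2.1).

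**Formulas.** Probability of at least one episode in d days: P(r, d) = 1 − exp(−r × d/365.25). For up-dosing of D days, the percentage is 0.8 × P(r, D) + 0.2 × M. M is the mean of P(r, t) for t uniform on 0 to D, that is, M = 1 − (1 − exp(−a))/a with a = rD/365.25.

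**Same rate in both periods, r = 0.3.**
- D = 140: 0.8 × 10.86% + 0.2 × 5.54% = 9.80%.
- D = 280: 0.8 × 20.55% + 0.2 × 10.67% = 18.57%.
- 300 mg QD, 14 days: P(0.3, 14) = 1.14%.

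| Rate per subject-year | Apparent fall, 20 vs 2 weeks | Apparent fall, 40 vs 2 weeks |
|---|---|---|
| 0.1 | 8.9-fold | 17.4-fold |
| 0.3 | 8.6-fold | 16.2-fold |
| 0.5 | 8.3-fold | 15.2-fold |

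At r = 0.3 with nobody leaving, the falls are 9.5- and 18.0-fold; with 30% leaving, 8.1- and 15.4-fold. The result is essentially the ratio of period lengths.

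**Rate doubled at 300 mg.** P(0.6, 14) = 2.27%, and 9.80/2.27 gives a 4.3-fold apparent fall. The two percentages become equal only at 2.69 per subject-year (D = 140) or 5.36 (D = 280), which is 9.0 or 17.9 times 0.3.

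**Longer 300 mg QD period (assumed delay), against 20-week up-dosing.** At 4, 8 and 16 weeks P is 2.27%, 4.50% and 8.79%, so the apparent fall is 4.3-, 2.2- and 1.1-fold. The contrast thus depends partly on how quickly sites activated the follow-on protocols.

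**AR101 against placebo within up-dosing, equal rates.** With one arm's exposure 20% shorter or 33% longer than 140 days, the ratio of percentages is 0.80 or 1.32 at r = 0.1, and 0.82 or 1.29 at r = 0.5.

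**Precision of the rate.** Two thirds of 500 is about 333 AR101 children. Leavers contribute half of up-dosing on average, so the factor is 0.8 + 0.2 × 0.5 = 0.9.
- Up-dosing: 333 × 0.9 × 140/365.25 = 114.9 subject-years. 34 episodes give 0.30 (exact 95% CI 0.20 to 0.41).
- 300 mg QD: 333 × 0.8 × 14/365.25 = 10.2 subject-years. 3 episodes give 0.29 (0.06 to 0.86); rate ratio 0.99 (conditional exact 95% CI 0.20 to 3.16).
- If the rate doubled, 6 episodes give 0.59 (0.22 to 1.28); rate ratio 1.99 (0.68 to 4.78).

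**The case against.** The strongest reply is that no planned analysis is harmed. The study is descriptive, no comparison of up-dosing with 300 mg QD is specified, and the intended contrast is AR101 beside placebo, where the distortion is small. The protocol asks for adjustment for treatment duration only for hypersensitivity events, and SAP 9.8.1 supplies it. Episode totals and exposure by period (SAP 9.5) are both planned, so a reader could work out a crude rate. All of this stands, and it is why the point is a suggested improvement and not a defect. It does not make the printed percentages comparable.

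A second reply is that SAP 9.8.1 may already cover the need, because its overall summary gives rates for events satisfying criteria that it does not list. Even if epinephrine were one of them, that summary counts adverse events. SAP 9.8.4 counts episodes within a 2-hour window, and SAP 9.8.5 counts food allergy episodes. Reactions that lead to epinephrine may sit within the hypersensitivity rates, but those rates do not separate the ones that needed it.

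A third reply is that a rate can also mislead. Up-dosing contains ten scheduled in-clinic dose increases and 300 mg QD contains none, only children who reached 300 mg contribute to the later period, and its rate is imprecise. These limits stand. A rate corrects for period length and nothing else.

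Finally, the secondary objective concerns treatment-related events, while a row of all epinephrine episodes is broader. That is fair. The split by relatedness already planned in SAP 9.8.4 lets the rate be scaled to related episodes.

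**Conclusion.** The concern holds, as a low-priority reporting weakness. Under a constant assumed rate of 0.1 to 0.5 per subject-year with 20% leaving, the planned tables would show an apparent 8.3- to 17.4-fold fall from up-dosing to a 2-week 300 mg QD period. The upper end needs the extreme of 40 weeks for everyone. SAP 7.1 says that some children stayed on 300 mg beyond the expected rollover date, so the real distortion may be smaller: about 1.1-fold if that period averaged 16 weeks. The event rate, the dropout and the delay are all assumptions. That the table can point the wrong way does not depend on their exact values, provided the 300 mg period is much the shorter one. A rate row would prevent that misreading but could not by itself establish that the rate changed.

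**What to change.** In SAP 9.8.4 and 9.8.5, add one supplementary row by arm for up-dosing, 300 mg QD and overall: total episodes per subject-year under the SAP 9.8.1 definition, with the subject-years shown. Base any statement comparing up-dosing with 300 mg QD on these rates, read with their imprecision. Keep percent of subjects as the measure for initial escalation, which lasts 1 or 2 days. Footnote that only children who reached 300 mg contribute to the 300 mg QD period, and that up-dosing mixes supervised dose increases with home dosing. Leave SAP 9.8.3 as it is.

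The cost is one row and a footnote in each of two tables. Episode totals and subject-years by period already come from SAP 9.8.4, 9.8.5, 9.8.1 and 9.5, so no new data or design change is needed.
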